- Currently active, clinically significant cardiovascular disease, such as uncontrolled arrhythmia or Class 3 or 4 congestive heart failure or a history of myocardial infarction, unstable angina, or acute coronary syndrome within 6 months prior to registration History of stroke or intracranial haemorrhage within 6 months prior to registration
- History of severe allergic or anaphylactic reactions to humanised or murine monoclonal antibodies. Known sensitivity or allergy to murine products.
- Vaccination with a live vaccine a minimum of 28 days prior to registration.
- Patients with Progressive Multifocal Leukoencephalopathy (PML).
- No known allergy to obinutuzumab or excipients

Cohort (B)i and (B)ii: Relapsed/refractory (initial phase – 20 patients, extension phase between 20-40 patients)

- Previous treatment with ibrutinib or an alternative inhibitor of B-Cell receptor pathway

Any patients currently participating in IcICLLe and wishing to consent for the IcICLLe extension study will need to meet the relevant eligibility criteria above

¹ Patients may be considered eligible if an active infection is being treated with a short course of antibiotics during the screening period. However, a patient cannot be registered and treated on the trial until the active infection has resolved and the antibiotics have stopped.

Sponsor

Cancer Research UK Clinical Trials Unit (CRCTU)
Institute of Cancer and Genomic Sciences
University of Birmingham
[name]

IcICLLe Contact Details:

IcICLLe Trial Coordinator
Haematology Team (TAP)
Postal Address: Centre for Clinical Haematology
Queen Elizabeth Hospital
[name]
[contact]
[contact]

Email: [contact]

Schedule of Events for IcICLLe**IcICLLe Treatment Schedule (initial phase) (Schedule A)**

Assessment	Screening	2 weeks prior to treatment	Day					Month					Every 6 months after 12 months	6 months after clinical complete or MRD negative remission ²	In the event of disease progression	
			1 Pre-treatment	1 (4 hr post 1 st dose)	2	8	15	1	3	6	9	12				
Demographic data, medical history, prior diagnosis/treatments	X															
Physical Examination (height, weight, BP, ECOG)	X				X			X	X	X	X	X	X	X	X	X
Constitutional symptom assessment	X							X		X					X	X
Clinical assessment of liver, spleen and lymph nodes		X			X			X	X	X	X	X	X	X	X	X
Disease response assessment								X		X					X	X
Local analysis	Haematology and biochemistry	X	X	X	X	X	X	X	X	X	X	X	X	X	X	X

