Participants will be recruited from TAP centres with expertise in the diagnosis and treatment of CLL. It is envisaged that all eligible patients at these centres will be offered the opportunity to participate in the study.

Assessment of response

Assessment of MRD will be carried out on peripheral blood samples throughout the study. It will be measured by flow and assessed using current IWCLL guidelines (refer to Appendix 1 for these guidelines and references). Assessment of MRD in bone marrow will be carried out on monotherapy patients after 6 months of continuous treatment with ibrutinib, and for combination therapy patients at 9 months (3 months after completion of combination therapy to allow for washout of antibodies). This is in line with comparable studies and IWCLL guidelines on assessment of MRD; that is to say that response should be assessed 2 months after the treatment has finished. Whilst extension study patients will continue on ibrutinib monotherapy after the 6 cycles of obinutuzumab, the effect of any synergy between ibrutinib and obinutuzumab should be evaluated after cessation of the second IMP. We can thus determine if administration of the combination therapy leads to a sustained response in patients when examining MRD in both peripheral blood at 1, 3, 6 and 9 months and bone marrow at 1 and 9 months.

Biological response will be assessed by way of peripheral blood and/or bone marrow examinations taken over a 12 month period. Further samples will also be collected every 6 months after this date, and 6 months after the patients achieve a clinical complete or MRD negative remission. If patients become confirmed MRD negative they will also stop treatment.

The key biological end-points will be complete following 6 months of trial treatment with secondary end-points of Modified IWCLL Response Criteria continuing to 12 months and beyond if patients continue to respond.

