7.2.2 Assessment schedule

Day 0 pre-ibrutinib treatment (cohort (B)ii only)

- Samples for central analysis
 - Peripheral blood sample 4 x 5 mL in EDTA
- Local laboratory tests
- Complete physical examination

Day 0 4 hrs post 1st ibrutinib treatment (cohort (B)ii only)

- Samples for central analysis
 - Peripheral blood 2 x 5mL in EDTA
- Local laboratory tests
- Local immunology

Day 1 (before the 1st obinutuzumab treatment)

- Samples for central analysis:
 - Peripheral blood 2 x 5mL in EDTA
- Complete physical examination
- Local laboratory tests

Day 2

- Samples for central analysis:
 - Peripheral blood 2 x 5mL in EDTA
- Complete physical examination

- Local laboratory tests

Day 8 and Day 15

- Samples for central analysis:
 - Peripheral blood 2 x 5mL in EDTA
- Local laboratory tests

Month 1

- Samples for central analysis (bone marrow samples not required for IcICLLe patients who have transitioned to the Extension Study):
 - Peripheral blood 4 x 5mL in EDTA
 - Bone Marrow Aspirate (EDTA)
 - Bone Marrow Trepine Biopsy (directly in formalin)
- Complete physical examination
- Constitutional symptom assessment
- ECG
- Local laboratory tests
- Disease Response according to modified IWCLL criteria (Appendix 1 & 2)

Month 3

- Samples for central analysis:
 - Peripheral blood 2 x 5mL in EDTA
- Complete physical examination
- Local laboratory tests
- CT scan

Month 6

Cohort (A) and B(i) (IcICLLe):

- Samples for central analysis:
 - Peripheral blood 4 x 5mL in EDTA
 - Bone Marrow Aspirate (EDTA)
 - Bone Marrow Trepine Biopsy (directly in formalin)
- Disease Response according to modified IWCLL criteria (Appendix 1 & 2)

Cohort (B)ii & (B)iii (IcICLLe Extension Study):

- Samples for central analysis
 - Peripheral blood 2 x 5mL in EDTA

All Cohorts

- Complete physical examination
- Constitutional symptom assessment
- Local laboratory
- Local immunology
- CT scan: should only be performed if the result of the 3 month scan was abnormal.

Month 9

Cohort (A) and (B)i (IcICLLe):

- Samples for central analysis:
 - Peripheral blood 2 x 5mL in EDTA

Cohort (B)ii & (B)iii (IcICLLe Extension Study):

- Samples for central analysis:
 - Peripheral blood 4 x 5mL in EDTA
 - Bone Marrow Aspirate (EDTA)
 - Bone Marrow Trepine Biopsy (directly in formalin)
- Disease Response according to modified IWCLL criteria (Appendix 1 & 2)

All Cohorts

- Complete physical examination
- Local laboratory tests

Month 12 and every 6 months thereafter

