- Samples for central analysis:
 - Peripheral blood 2 x 5mL in EDTA
- Complete physical examination
- Local laboratory tests

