7.2.4 Assessments at disease progression

Patients will be evaluated at disease progression. Disease progression will be defined using the Modified IWCLL Response Criteria (2008) given in Appendix 2.

Progressive disease during or after any period of therapy is characterised by at least one of the following:

- Lymphadenopathy

¹⁵ Defined as months from date of registration to the Extension Study

- An increase in the liver or spleen size by 50% or more and the *de novo* appearance of hepatomegaly or splenomegaly.
- An increase in the number of blood lymphocytes by 50% or more with at least $5 \times 10^9/L$ B lymphocytes (not before at least 12 months of therapy when the lymphocytosis is expected and is treatment related).
- Transformation to a more aggressive histology (e.g., Richter syndrome). Whenever possible this diagnosis should be established by lymph node biopsy.
- Occurrence of cytopenia (neutropenia, anaemia, or thrombocytopenia) attributable to CLL.

The following assessments should be undertaken:

- Samples for central analysis:
 - Peripheral blood 4 x 5mL in EDTA
 - Bone Marrow Aspirate (EDTA)
 - Bone Marrow Trephine Biopsy (directly in formalin)
- Complete physical examination
- Constitutional symptom assessment
- CT-scan Local blood biochemistry and haematology
- Local immunology

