12.1.2 Secondary Objectives / Outcome Measures

- Best disease response, whether complete remission (CR), complete remission with incomplete marrow recovery (Cri) or partial remission (PR), to treatment in a) the initial phase of the study at or before the 6 month assessment and b) the Extension Study at or before the 9 month assessment. Independent decisions will be made for each study (initial and extension)., assessed according to the IWCLL Criteria (revised 2008) (Appendix 1). The dynamics of response will be assessed both in terms of the change in absolute levels of CLL in the blood and marrow as well as the changes in the proliferating compartment and changes in chemokine receptor.
- 1 and 2 year progression free survival for relapsed/refractory and treatment naïve patients defined as time from date of registration to date of progression (per the modified 2008 IWCLL criteria) or death from any cause. Alive patients who are progression free will be censored at their date of last follow-up.
- 1 and 5 year overall survival for relapsed/refractory and treatment naïve patients is defined as the time from date of registration to the date of death from any cause.
- Toxicity of ibrutinib and obinutuzumab
- CLL cell levels as a percentage of total leucocytes in the bone marrow (BM) and absolute counts in the peripheral blood (PB).
- The proportion of patients with >5%, 0.5-5%, <0.5% CLL cells in cell cycle (expressing Ki67) in the peripheral blood and bone marrow in a) the initial phase of the study at or before the 6 month assessment and b) the Extension Study at or before the 9 month assessment
- Change in the expression levels of CD10, CD103, CD11c, CD185, CD196, CD20, CD200, CD22, CD23, CD25, CD27, CD305, CD31, CD38, CD39, CD43, CD49d, CD5, CD79b, CD81, CD95, IgD, IgG, or IgM on CLL cells relative to baseline by more than 50% and at least 500 arbitrary units in median fluorescence intensity.

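### Section 3 carries modified IWCLL response to 12 months and beyond, but no formal response item is scheduled after Month 6 or Month 9, and PFS is censored at last follow-up rather than last disease assessment

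*Protocol*

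**What the plan says.** - **Section 3 (Assessment of response):** the key biological end-points finish at 6 months, with "secondary end-points of Modified IWCLL Response Criteria continuing to 12 months and beyond if patients continue to respond".
- **Schedules A and B:** the row "Disease response assessment" is marked at Months 1 and 6 in Schedule A and Months 1 and 9 in Schedule B. In both it is also marked 6 months after remission and at progression. It is not marked at Month 12 or at the 6-monthly visits.
- **The same schedules:** the separate row "Clinical assessment of liver, spleen and lymph nodes" is marked at Months 1, 3, 6, 9 and 12, every 6 months after that, and at progression. Physical examination and local haematology and biochemistry also continue.
- **Section 7.2.2:** under "Month 12 and every 6 months thereafter" it lists central peripheral blood, "Complete physical examination" and local laboratory tests. There is no disease response line, although there is one at Month 1 and at Month 6 or 9.
- **Section 7.2.4:** "Patients will be evaluated at disease progression", followed by the criteria and the work-up.
- **Section 12.1.2:** best response is fixed at or before 6 months (initial) or 9 months (extension). A further secondary outcome is "1 and 2 year progression free survival for relapsed/refractory and treatment naïve patients defined as time from date of registration to date of progression" or death, by the modified criteria. The censoring rule is "Alive patients who are progression free will be censored at their date of last follow-up".

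**The concern.** Section 3 and the operative schedule disagree. One says that assessment against the modified criteria goes on past 12 months. The other stops the formal item at Month 6 or 9. The protocol treats measuring the disease and classifying response as separate rows, so continued measurement does not by itself produce a recorded IWCLL status.

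Two features make this matter for PFS. First, the lymphocyte criterion in section 7.2.4 applies only after at least 12 months of therapy, so it becomes usable after formal classification has stopped. Second, the censoring date is last follow-up. Section 7.10 follows patients until death, so a contact that establishes survival but involves no disease evaluation can extend progression-free time.

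At stake are the traceability of response beyond 6 or 9 months and a small upward risk in 1- and 2-year PFS, in a trial whose results are to inform a randomised one.

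**Working it through.** **No figure to reproduce.** The protocol gives no sample size, power or event count for PFS. The check is a comparison of passages, then an illustration of size under stated assumptions.

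**Step 1: count the scheduled items after the last formal assessment, up to Month 24.**

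| | Initial phase (after Month 6) | Extension (after Month 9) |
|---|---|---|
| Routine formal disease response items | 0 | 0 |
| Visits with node, liver and spleen assessment plus counts | 4 (Months 9, 12, 18, 24) | 3 (Months 12, 18, 24) |

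The schedule tables were machine-read and their columns are broken, but this reading agrees with section 7.2.2.

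**Step 2: set the later visits against the progression criteria in section 7.2.4.** Section 7.2.1 requires nodes to be measured in two dimensions, and liver and spleen if palpable, at each clinical assessment. Together with blood counts, this informs the node, organ, lymphocyte and cytopenia criteria. Transformation can be suspected and then biopsied. No routine CT is marked after Month 6 outside remission and progression, so progression visible only on imaging could be found late.

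**Step 3: how much could PFS rise if visits miss some progressions?** Assumptions, none from the protocol: exponential progression, deaths ignored, true 2-year PFS of 60%, 75% or 90%, and a fixed chance that a visit detects existing progression. From the protocol: visits at Months 1, 3, 6, 9, 12, 18, 24 and 6-monthly after, each within 7 days either way. True 1-year PFS is the square root of the 2-year value, for example √0.75 = 0.866. Apparent PFS is read at 12.25 and 24.25 months, just after the visit window (7/30.4 = 0.23 month). There were 400,000 simulated times per case.

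| True 1-year / 2-year PFS | Full detection | 80% per visit | 50% per visit |
|---|---|---|---|
| 77.5% / 60% | 77.4 / 60.0 | 78.8 / 61.9 | 82.5 / 67.6 |
| 86.6% / 75% | 86.6 / 75.0 | 87.4 / 76.3 | 89.6 / 80.1 |
| 94.9% / 90% | 94.8 / 89.9 | 95.2 / 90.6 | 96.0 / 92.1 |

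The 2-year excess is about 0 points with full detection and 0.6 to 1.9 points at 80%. It reaches 2.1 to 7.6 points only if half of existing progressions are missed at every visit.

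**Step 4: direction of the censoring rule.** Take a cohort of 20 (section 12.5.1) with all at risk when one progression occurs. The Kaplan-Meier factor is 19/20 = 0.950. Suppose two of those patients have had only contact since their last disease assessment. Censored at that assessment, they leave the risk set and the factor is 17/18 = 0.944. The rule as written is higher by 0.6 point. The two patients are hypothetical; the example shows direction and scale only.

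**The case against.** The strongest reply is that disease is assessed throughout. Measured nodes, liver, spleen and counts continue at Month 12 and 6-monthly. Treatment runs until progression by the modified criteria (section 7.1), so progression has to be judged for treatment to continue. The CRF is not shown, so a missing status field cannot be inferred. All of this stands.

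It disposes of a stronger reading that a reader might infer: that no disease assessment takes place after Month 6 or 9, so patients go unassessed and count as progression-free. If nothing were found after those months, a true 2-year PFS of 75% would read 0.75^(6/24) = 93.1% or 0.75^(9/24) = 89.8%. The schedules rule that situation out.

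A reader might also infer an excess of 4 to 7 points at 2 years by dating progression at visits and assuming 3 to 14 days from registration to first dose. The protocol gives no such lag; sections 3 and 7.1 start ibrutinib from registration. With no lag, the same model reads 0.823 against a true 0.800, about 2 points, because some Month 24 visits fall just past the landmark. Since that model already assumes detection at these visits, it does not measure the effect of the missing response item. How to read the curve at a landmark can be left to the SAP.

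Sampling error is also far larger than the likely bias. With 20 patients at 80%, the normal-approximation half-width is 1.96 × √(0.8 × 0.2/20) = 0.175, and the initial-phase analysis is descriptive only.

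Finally, section 3 can be read together with PFS, which 12.1.2 defines by the modified criteria, so the 6/9-month best-response window need not change. That is fair. But this reading still needs status against those criteria at the later visits, and the schedule does not ask for it. The choice of censoring date could likewise have been left to the SAP, but the protocol fixes it.

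**Conclusion.** The contradiction holds. Section 3 describes modified IWCLL assessment to 12 months and beyond, while Schedules A and B and section 7.2.2 schedule no routine formal classification after Month 6 or 9. Progression can still be recognised from the examinations and counts that continue. What is missing is a scheduled, recorded status and a censoring date tied to it.

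The effect on 1- and 2-year PFS is upward in direction and likely small. The documents do not quantify it. The figures of about 0 to 2 points at 2 years rest on assumed exponential progression and 80 to 100% detection per visit. The documents do not support a claim that PFS is materially overstated. This is a minor to moderate inconsistency, worth correcting because the correction is nearly free.

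**What to change.** 1. In section 7.2.2 and Schedules A and B, add disease status by the modified IWCLL criteria at Month 12 and each 6-monthly visit, judged from the examination and counts already taken. No extra CT or marrow is needed. This gives the statement in section 3 a scheduled source.
2. In section 12.1.2, censor patients who are alive and progression-free at their last such disease assessment instead of at last follow-up.
3. Leave the best-response window at 6 months (initial) and 9 months (extension). State in section 3 that later status serves PFS and duration of response, not best response.

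The cost is a wording amendment, one CRF item per visit and slightly earlier censoring, which gives up a little follow-up time in the PFS estimate.

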3.1 Translational Studies

The studies described below are optional translational studies.

3.1.1 Kinetics Sub Study (Appendix 8):

This sub-study will be run alongside the IcICLLe trial at a limited number of centres.

If your centre is running the Kinetics Sub Study, patients should be given the option to participate in a 'Kinetics Study', which will run alongside IcICLLe and will be based at King's College Hospital London. An assessment of tumour proliferation rate will be assessed using flow sorted CLL cells and will measure proliferation by the in-vivo incorporation of deuterated glucose ($^2\text{D-Glc}$) into the leukemic cells.

3.1.2 Biobanking of samples with the UK CLL Trials Biobank (Appendix 9):

Patients taking part in the IcICLLe trial may also be approached to donate samples to the UK CLL Trials Biobank. This is separate research involving

4. ELIGIBILITY

4.1 Inclusion Criteria

Cohort (A): Treatment naïve (initial phase only – 20 patients)

- Progressive Stage A, Stage B or Stage C CLL (Appendix 7)
- CLL requiring therapy by the IWCLL criteria (Appendix 1)
- ECOG performance status (PS) of 0, 1, or 2 (Appendix 6)
- Life expectancy of at least 6 months
- Age ≥ 18
- Prepared to undergo the stipulated investigations within the trial (including bone marrow examinations)
- Able to give informed consent
- Adequate hepatic function, defined as serum aspartate transaminase (AST) or alanine transaminase (ALT) $< 2.5 \times \text{ULN}$, and total bilirubin $\leq 1.5 \times \text{ULN}$ unless due to Gilbert's syndrome
- Adequate renal function, defined as estimated creatinine clearance $\geq 30 \text{ ml/min}$ using the Cockcroft-Gault equation

Cohort (B)i and (B)ii: Relapsed/refractory (initial phase – 20 patients, extension phase between 20-40 patients)

- B-CLL requiring therapy according to the IWCLL guidelines
 - The leukaemia cells should co-express CD19, CD5, and CD23 and each clone should have restricted to expression of either kappa or lambda immunoglobulin light chains.
 - The levels of surface immunoglobulin, CD20, and CD79b should be low. If there is atypically strong surface immunoglobulin, CD20, or CD79b expression, or other atypical features, it may not be possible to perform the MRD monitoring required to evaluate the primary endpoint.¹²
- Refractory/relapsed CLL defined as any of the following:
 - Failure to achieve a response (CR or PR by IWCLL Criteria) to a purine analogue alone or in combination with chemotherapy, or:
 - Relapse within 6 months of responding to a purine analogue alone or in combination with chemotherapy, or:
 - Relapse at any time after fludarabine, cyclophosphamide and rituximab (FCR) or bendamustine plus rituximab, or:
 - Patients with CLL with deletion of chromosome 17p who have failed at least one previous therapy.
- ECOG PS of 0, 1, or 2 (see Appendix 6)
- Life expectancy of at least 6 months
- Prepared to undergo the stipulated investigations within the trial (including bone marrow examinations)
- Age ≥ 18
- Able to give informed consent
- Ability to comply with study protocol procedures
- Adequate hepatic function, defined as serum aspartate transaminase (AST) or alanine transaminase (ALT) $< 2.5 \times \text{ULN}$, and total bilirubin $\leq 1.5 \times \text{ULN}$ unless due to Gilbert's syndrome
- Adequate renal function, defined as estimated creatinine clearance $\geq 30 \text{ mL/min}$ using the Cockcroft-Gault equation
- Minimum platelet count of $\geq 50 \times 10^9/\text{L}$
- Absolute neutrophil count $\geq 1.0 \times 10^9/\text{L}$ (unless due to direct marrow infiltration by CLL (to be confirmed via bone marrow biopsy))

Cohort (B)iii: Ibrutinib treated patients (extension phase only – up to 20 patients)

Patients enrolled on the IcICLLe trial as relapsed/refractory patients who have received treatment with Ibrutinib on the IcICLLe trial for at least 6 months

¹² If there are known to be any atypical features, please send a peripheral blood to HMDS for evaluation at least two weeks prior to the screening bone marrow sample.

